10.3.1. Efficacy Analysis

The primary endpoint for Cohorts 1-6: the proportion of participants whose left buttock (investigational side) demonstrates at least a 1-level lower score versus the right buttock (control side) on the IABSS, at Visit 3 will be summarized by cohort using appropriate descriptive statistics. In addition, the counts and percentages for each severity scale will be summarized by cohort and treatment area.

The primary endpoint for Cohort 7a: The proportion of participants whose left buttock (investigational side), at Visit 3, demonstrates at least 1-level lower score versus the right buttock (control side), at Visit 8 on the IABSS will be summarized by cohort using appropriate descriptive statistics. In addition, the counts and percentages for each severity scale will be summarized by cohort and treatment area.

The primary endpoint for Cohort 7b: The proportion of participants whose left buttock (investigational side), at Visit 8, demonstrates at least 1-level lower score versus the right buttock (control side), at Visit 3, on the IABSS will be summarized by cohort using appropriate

descriptive statistics. In addition, the counts and percentages for each severity scale will be summarized by cohort and treatment area.

For Cohorts 1-6, at each visit the proportion of participants whose left buttock (investigational side) demonstrates at least a 1 level lower score versus the right buttock (control side) on the IABSS will be summarized by cohort using appropriate descriptive statistics. In addition, the counts and percentages for each severity scale at each visit will be summarized by cohort and treatment area.

For Cohorts 7a and 7b: The proportion of participants whose left buttock (investigational side) demonstrates at least 1-level lower score versus the right buttock (control side), on the IABSS will be summarized by cohort using appropriate descriptive statistics at the corresponding treatment visit (first dose of QWO [CCH-aaes] on the investigational buttock with tranexamic acid vs the first dose of QWO [CCH-aaes] without tranexamic acid on the control side; second dose of QWO [CCH-aaes] on the investigational buttock vs second dose of QWO [CCH-aaes] on the control side; third dose of QWO [CCH-aaes] on the investigational side vs third dose of QWO [CCH-aaes] on the control side); and at each follow up visit thereafter.

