4.5. Efficacy Parameters

4.5.1. IABSS Ratings

The IABSS rating is directly obtained from the investigator's assessments at treatment visits and their corresponding follow-up visits, ie, Visit 1 (Day 1) through Visit 15 (Day 57) for Cohorts 1-5, Visit 1 (Day 1) through Visit 11 (Day 57) for Cohort 6, and Visit 1 (Day 1) through Visit 20 (Day 78) for Cohort 7.

For the primary and secondary analysis, the following definition will be used for Cohorts 1 to 7 for the primary endpoint: A one-level IABSS responder at Visit A versus Visit B is defined as the participant whose left buttock (investigational side) at Visit A demonstrates at least a 1-level lower IABSS score versus the right buttock (control side) at Visit B, where Visit A and B can either be same or different.

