7.6.1. Primary Analysis

7.6.1.1. Cohort 1-6: The proportion of one-level IABSS responders, at Visit 3, three to five days after initial QWO (CCH-aaes) injection.

The primary estimand for cohort 1 to 6 is defined by the following:

- The *primary* clinical question of interest is: In adult female participants with moderate to severe cellulite, what is the proportion of participants in Cohort 1-6, whose left buttock (investigational side) demonstrates at least 1-level lower IABSS score versus the right buttock (control side) on the IABSS, at Visit 3, 3 to 5 days after initial QWO (CCH-aaes) injection?
- **Treatment condition:** Participants will be assigned to 1 of 6 cohorts.
- Target Population: Adult females with a CR-PCSS score of 3 or 4 on both buttocks, Hexsel CSS \leq 12, with a BMI of 18 to < 32 kg/m² (normal or overweight) and Fitzpatrick skin type of I-IV who are included in the FAS.
- Variable (Endpoint) of interest: Proportion of one-level IABSS responders at Visit 3, 3 to 5 days after initial QWO (CCH-aaes) injection for Cohort 1-6. Refer to Section 4.5.1 for one-level IABSS responder definition.
- Treatments being compared: The labelled dose and concentration will be compared to administering the labelled dose or lower doses in different diluent additives, concentrations, depths of injection, and methods of injection (refer to Table 2).
- Intercurrent Event: Not applicable.
- **Population Level-Summary measure:** Not applicable.

- **Method of Analyses:** The one-level IABSS responders will be summarized for each cohort using frequency, proportion and corresponding 95% CI based on the Clopper-Pearson method for one-level IABSS responders at Visit 3, 3 to 5 days after the initial QWO (CCH-aaes) injection for Cohort 1-6.
- Supportive analysis to primary endpoint: Not applicable.

IABSS ratings will be summarized by treatment area at each visit for all 7 cohorts and overall. A listing of IABSS ratings by participant will be provided.

7.6.1.2. Cohort 7a: The proportion of one-level IABSS responders, at Visit 3 versus Visit 8, three to five days after initial QWO (CCH-aaes) injection at respective visit.

The primary estimand for cohort 7a is defined by the following:

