- Variable (Endpoint) of interest: Proportion of one-level IABSS responders at Visit 8 versus Visit 3, 3 to 5 days after initial QWO (CCH-aaes) injection for each respective visit for Cohort 7b. Refer to Section 4.5.1 for one-Level IABSS responder definition.
- **Treatments being compared:** The labelled dose and concentration will be compared to administering the labelled dose or lower doses in different diluent additives, concentrations, depths of injection, and methods of injection (refer to Table 2).
- Intercurrent Event: Not applicable.
- Population Level-Summary measure: Not applicable.
- **Method of Analyses:** The one-level IABSS responders will be summarized for each cohort using frequency, proportion and corresponding 95% CI based on the Clopper-Pearson method for one-level IABSS responders at Visit 8 versus Visit 3, 3 to 5 days after initial QWO (CCH-aaes) injection for each respective visit for Cohort 7b.
- Supportive analysis to primary endpoint: Not applicable.

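### The IABSS responder proportion counts one direction only, and the readable SAP plans no lower/same/higher count or paired interval to set beside it

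*SAP*

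**What the plan says.** SAP 4.5.1 defines a responder as a participant whose left (investigational) buttock "at Visit A demonstrates at least a 1-level lower IABSS score versus the right buttock (control side) at Visit B". The two visits are the same in Cohorts 1-6 and differ in 7a and 7b. The method in 7.6.1.1 to 7.6.1.3 is "The one-level IABSS responders will be summarized for each cohort using frequency, proportion and corresponding 95% CI based on the Clopper-Pearson method", and 7.6.2.1 and 7.6.2.2 use it again for the by-visit IABSS endpoints.

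Each of these estimands states a comparison: "The labelled dose and concentration will be compared to administering the labelled dose or lower doses in different diluent additives". Each then gives "Population Level-Summary measure: Not applicable". The primary ones add "Supportive analysis to primary endpoint: Not applicable", and the secondary ones have a matching line.

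Two other outputs bear on the point. SAP 7.6.1.1 says "IABSS ratings will be summarized by treatment area at each visit for all 7 cohorts and overall" and "A listing of IABSS ratings by participant will be provided". Protocol 10.3.1 likewise plans that "counts and percentages for each severity scale will be summarized by cohort and treatment area", and it describes the analysis as descriptive throughout.

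**The concern.** The primary objective is to assess the effect of the interventions on bruising. Two buttocks rated on a five-point scale will sometimes differ by a level with no intervention effect, and about half of those differences will favour the investigational side. A proportion that counts only those has a no-effect value above zero. That value depends on how often the two sides tie, which the plan neither states nor tabulates. The number of participants who did worse decides how a given responder rate should be read, and that number is merged with the ties.

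Protocol 7.1 asks for equal injection numbers on Day 1, which should reduce chance asymmetry in the cohorts it covers (1, 2, 3, 5 and 6). It does not make the reference zero. It does not apply in Cohort 4, where the design allows up to 30 injections on the investigational side and up to 12 on the control side (protocol 5.1 and 7.1).

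**Working it through.** **Inputs from the documents.** Up to 30 participants per cohort and 15 each in 7a and 7b (6 × 30 + 2 × 15 = 210, as stated); the responder definition (SAP 4.5.1); the Clopper-Pearson 95% CI (SAP 7.6.1). No power, reference rate or tie rate is given, so the plan has no figure for this endpoint to reproduce.

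**Assumption.** Tie rate t from 80% to 40%, with lower and higher equally likely when there is no effect.

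**Step 1: the no-effect value.** Expected responder proportion = (1 - t)/2. The last column is the binomial probability of 9 or more responders in 30.

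| Tie rate t | (1 - t)/2 | P(9 or more of 30), no effect |
|---|---|---|
| 80% | 10% | 0.2% |
| 70% | 15% | 2.8% |
| 60% | 20% | 12.9% |
| 50% | 25% | 32.6% |
| 40% | 30% | 57% |

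**Step 2: one primary result, several meanings.** The planned output for 9/30 is 30.0%, CI 14.7% to 49.4%. The net difference is (lower - higher)/n, with a Tango score 95% CI and an exact two-sided sign test.

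| Lower / same / higher | Net difference (95% CI) | Sign test p |
|---|---|---|
| 9 / 21 / 0 | +30% (15.2% to 47.9%) | 0.004 |
| 9 / 18 / 3 | +20% (-2.9% to 41.2%) | 0.146 |
| 9 / 12 / 9 | 0% (-27.1% to 27.1%) | 1.00 |

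The planned proportion and CI are identical in all three rows.

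**Step 3: do the by-side tables settle it?** If both sides are always rated and every difference is one level, yes: higher = lower - n × mean difference. Mean differences of 0.30, 0.20 and 0 then give 0, 3 and 9 worse. If some differences are two levels, not in general. Take control-side counts of 6/20/4 at levels 1/2/3 and investigational-side counts of 11/19 at levels 1/2, so the mean difference is 9/30 = 0.30. Pairs below are (control, investigational) × count.

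- A: (3,2)×4, (2,1)×5, (1,1)×6, (2,2)×15. This gives 9 lower, 21 same, 0 higher: net +30% (15.2% to 47.9%), p = 0.004.
- B: (3,1)×4, (2,1)×5, (1,2)×4, (1,1)×2, (2,2)×15. This gives 9 lower, 17 same, 4 higher: net +16.7% (-7.3% to 38.9%), p = 0.267.

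Both produce the same two by-side tables and the same 9/30. The FAS (SAP 5) requires a valid rating at only one treatment area, and SAP 6.1 uses non-missing denominators, so the two sides can also rest on different participants.

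**Step 4: n = 15.** With 5 lower and 0 higher, the Tango interval is 6.1% to 58.3% while the exact sign test gives p = 0.0625. A paired interval in 7a or 7b is therefore approximate.

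**The case against.** The plan answers the question it asks. That question is a proportion, the analysis is descriptive, and the readable text sets no null hypothesis, threshold or power for it. With at most 30 listed pairs per cohort, anyone can count the worse participants. The by-side tables show direction and mean difference, and SAP 6.1 already says that participants removed from an analysis are footnoted with reasons. The tie rates in step 1 are assumed. Example B is constructed, and part of its contrast with A arises because the sign test treats a two-level gain like a one-level loss: a paired t-test on B gives p = 0.07 for the same mean of 0.30. A lower/same/higher row could also sit in the table shells (SAP 11, Module 2) or in the redacted exploratory method (SAP 7.6.3).

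Most of this stands, and it limits the point to the absence of a pre-specified paired summary in the readable plan. It does not remove that gap. The supportive-analysis lines for the named estimands are readable and say that none applies. A listing leaves the count to be made after the data are known, and by-side tables carry no paired interval.

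A reader might infer that the trial cannot show whether an intervention reduces bruising, or that it would declare success on chance. The documents support neither. Both ratings are collected and listed, and no success rule exists for chance to satisfy.

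**Conclusion.** The point holds in limited form. As the readable SAP stands, the responder proportion and its interval do not by themselves separate benefit from chance left-right differences. The no-effect value is 10% to 30% under the assumed tie rates, and a single result of 9/30 is compatible with net differences from +30% to zero. This rests on symmetric differences under no effect and on tie rates that the documents do not supply. It is a weakness in how the primary result can be read. It is not a calculation error or a loss of data, and it claims nothing about the redacted or unseen material. The weight is minor to should-fix; the case for acting is that the improvement is cheap.

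**What to change.** Keep the responder proportion as the primary endpoint and enter it in the population-level summary line, so that the estimand still matches the protocol endpoint. In the supportive-analysis line of SAP 7.6.1.1-7.6.1.3 and 7.6.2.1-7.6.2.2, replace the present entry with:

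1. A lower/same/higher table by cohort, among participants with both sides rated.
2. P(at least 1 level lower) minus P(at least 1 level higher) with a paired 95% CI (for example the Tango score interval), labelled descriptive.

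For 7a and 7b, add that the sides are rated at different visits, so the contrast also carries any period effect; that the two sub-cohorts have mirrored treatment order and should be read side by side; and that the interval is approximate at n = 15. State that fixed left-side assignment and open-label rating remain limitations, which a paired contrast does not remove.

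The cost is SAP wording and a few extra table rows from ratings already collected. It needs no extra participants or visits and no change to the protocol endpoint. The tables become slightly longer, and the descriptive label is needed so that the interval is not read as a test.

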7.6.2. Secondary Efficacy Endpoints

7.6.2.1. Secondary Endpoint 1: The proportion of participants whose left buttock (investigational side) demonstrates at least 1-level lower score versus the right buttock (control side) on the IABSS, by visit.

The 1st secondary estimand is defined by following:

- The secondary clinical question of interest is: In the adult female participants with moderate to severe cellulite, what is the proportion of participants in Cohort 1-6 whose left buttock (investigational side) demonstrates at least 1-level lower score versus the right buttock (control side) on the IABSS, at each visit?
- **Treatment condition:** Participants will be assigned to 1 of 6 cohorts.
- Target Population: Adult females with a CR-PCSS score of 3 or 4 on both buttocks, Hexsel CSS ≤ 12, with a BMI of 18 to < 32 kg/m² (normal or overweight) and Fitzpatrick skin type of I-IV who are included in the FAS.
- Variable (Endpoint) of interest: In Cohort 1-6, proportion of one-level IABSS responders at each visit. Refer to Section 4.5.1 for one-level IABSS responder definition.

- Treatments being compared: The labelled dose and concentration will be compared to administering the labelled dose or lower doses in different diluent additives, concentrations, depths of injection, and methods of injection (refer to Table 2).
- Intercurrent Event: Not applicable.
- Population Level-Summary measure: Not applicable.
- **Method of Analyses:** The one-level IABSS responders will be summarized for each cohort using frequency, proportion and corresponding 95% CI based on the Clopper-Pearson method for one-level IABSS responders. For Cohort 1-5, the summary tables will be given for Visit 2-Visit 15 and for Cohort 6 it will be for Visit 2-Visit 11.
- Supportive analysis to secondary endpoint: Not applicable.
- 7.6.2.2. Secondary Endpoint 1: The proportion of participants within each cohort (ie, 7a and 7b) whose left buttock (investigational side) demonstrates at least 1-level lower score versus the right buttock (control side), on the IABSS, by corresponding treatment visit by buttock and at each follow up visit thereafter.

The 2nd secondary estimand is defined by following:

- The secondary clinical question of interest is: In the adult female participants with moderate to severe cellulite, what is the proportion of participants within Cohort 7a and 7b whose left buttock (investigational side) demonstrates at least 1-level lower score versus the right buttock (control side), on the IABSS, by corresponding treatment visit by buttock (first dose of QWO [CCH-aaes] on the investigational buttock with tranexamic acid vs the first dose of QWO [CCH-aaes] without tranexamic acid on the control side; second dose of QWO [CCH-aaes] on the investigational buttock vs second dose of QWO [CCH-aaes] on the control side; third dose of QWO [CCH-aaes] on the investigational side vs third dose of QWO [CCH-aaes] on the control side); and at each follow up visit thereafter?
- **Treatment condition:** Participants will be assigned to Cohort 7a and 7b.
- Target Population: Adult females with a CR-PCSS score of 3 or 4 on both buttocks, Hexsel CSS \leq 12, with a BMI of 18 to < 32 kg/m² (normal or overweight) and Fitzpatrick skin type of I-IV who are included in the FAS.
- Variable (Endpoint) of interest: In Cohort 7, proportion of one-level IABSS responders, by corresponding treatment visit by buttock (first dose of QWO [CCH-aaes] on the investigational buttock with tranexamic acid vs the first dose of QWO [CCH-aaes] without tranexamic acid on the control side; second dose of QWO [CCH-aaes] on the investigational buttock vs second dose of QWO [CCH-aaes] on the control side; third dose of QWO [CCH-aaes] on the investigational side vs third dose of QWO [CCH-aaes] on the control side); and at each follow up visit thereafter. Refer to Section 4.5.1 for one-level IABSS responder definition.
- Treatments being compared: The labelled dose and concentration will be compared to administering the labelled dose or lower doses in different diluent additives, concentrations, depths of injection, and methods of injection (refer to Table 2).

- Intercurrent Event: Not applicable.
- **Population Level-Summary measure:** Not applicable.
- **Method of Analyses:** The one-level IABSS responders will be summarized for each cohort using frequency, proportion and corresponding 95% CI based on the Clopper-Pearson method for one-level IABSS responders at Visit 2-Visit 20 for Cohort 7a and 7b.
- Supportive analysis to secondary endpoint: Not applicable.
- 7.6.2.3. Secondary Endpoint 2: The proportion of participants with an improved (+1 or better) score on the Investigator-Global Aesthetic Improvement Scale (I-GAIS) by treatment area for Cohort 1-5 at Visit 6 (Day 22), Visit 11 (Day 43), Visit 16 (Day 90), Visit 17 (Day 135) and Visit 18 (Day 180). For Cohort 6 at Visit 7 (Day 43), Visit 12 (Day 90), Visit 13 (Day 135) and Visit 14 (Day 180) and for Cohort 7 at Visit 6 (Day 22), Visit 11 (Day 43), Visit 16 (Day 64), Visit 21 (Day 90), Visit 22 (Day 135) and Visit 23 (Day 180).

The 3rd secondary estimand is defined by following:

- The secondary clinical question of interest is: In the adult female participants with moderate to severe cellulite, what is the proportion of participants with an improved (+1 or better) score on I-GAIS for each treatment area for Cohort 1-5 at Visit 6 (Day 22), Visit 11 (Day 43), Visit 16 (Day 90), Visit 17 (Day 135) and Visit 18 (Day 180); for Cohort 6 at Visit 7 (Day 43), Visit 12 (Day 90), Visit 13 (Day 135) and Visit 14 (Day 180) and for Cohort 7 at Visit 6 (Day 22), Visit 11 (Day 43), Visit 16 (Day 64), Visit 21 (Day 90), Visit 22 (Day 135) and Visit 23 (Day 180)?
- **Treatment condition:** Participants will be assigned to 1 of 7 cohorts.
- Target Population: Adult females with a CR-PCSS score of 3 or 4 on both buttocks, Hexsel CSS ≤ 12, with a BMI of 18 to < 32 kg/m² (normal or overweight) and Fitzpatrick skin type of I-IV who are included in the FAS.
- Variable (Endpoint) of interest: Proportion of one-level I-GAIS responders for Cohort 1-5 at Visit 6 (Day 22), Visit 11 (Day 43), Visit 16 (Day 90), Visit 17 (Day 135) and Visit 18 (Day 180). For Cohort 6 at Visit 7 (Day 43), Visit 12 (Day 90), Visit 13 (Day 135) and Visit 14 (Day 180) and for Cohort 7 at Visit 6 (Day 22), Visit 11 (Day 43), Visit 16 (Day 64), Visit 21 (Day 90), Visit 22 (Day 135) and Visit 23 (Day 180). Refer to Section 4.5.2 for one-level I-GAIS responder definition.
- **Treatments being compared:** The labelled dose and concentration will be compared to administering the labelled dose or lower doses in different diluent additives, concentrations, depths of injection, and methods of injection (refer to Table 2).
- Intercurrent Event: Not applicable.
- Population Level-Summary measure: Not applicable.

- Method of Analyses: The one-level I-GAIS responders will also be summarized by treatment area for each cohort using frequency, proportion and corresponding 95% CI based on the Clopper-Pearson method for one-level I-GAIS responders. The summary tables will be provided for Cohort 1-5 at Visit 6 (Day 22), Visit 11 (Day 43), Visit 16 (Day 90), Visit 17 (Day 135) and Visit 18 (Day 180). For Cohort 6 at Visit 7 (Day 43), Visit 12 (Day 90), Visit 13 (Day 135) and Visit 14 (Day 180) and for Cohort 7 at Visit 6 (Day 22), Visit 11 (Day 43), Visit 16 (Day 64), Visit 21 (Day 90), Visit 22 (Day 135) and Visit 23 (Day 180).
- Supportive analysis to secondary endpoint: Not applicable.

I-GAIS ratings will be summarized for Cohort 1-5 at Visit 6 (Day 22), Visit 11 (Day 43), Visit 16 (Day 90), Visit 17 (Day 135), and Visit 18 (Day 180). For Cohort 6 at Visit 7 (Day 43), Visit 12 (Day 90), Visit 13 (Day 135), and Visit 14 (Day 180) and for Cohort 7 at Visit 6 (Day 22), Visit 11 (Day 43), Visit 16 (Day 64), Visit 21 (Day 90), Visit 22 (Day 135) and Visit 23 (Day 180) by treatment area for each of the cohorts. The I-GAIS ratings by participant at each visit will be listed.

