- ⁿ Serious adverse events (SAEs) and adverse events (AEs) will be collected by the investigator from the time of signing the informed consent through the Day 180 EOS/ET Visit. All ongoing AEs must be followed until they have resolved or for 28 days after the participant's last treatment visit, whichever comes first. For participants who withdraw from the study early, SAEs and AEs will be collected for 28 days after the last dose of QWO (CCH-aaes).
- º Participants are encouraged to remain in the study for follow-up until the Day 180 Visit. Participants who discontinue from the study or study intervention and do not agree to remain in the study for follow-up until Day 180, will be asked to complete an early termination (ET) visit and a 28-day post-treatment Safety Follow-up Visit (or phone call if a visit is not possible) if applicable. The status of any ongoing AEs/SAEs or the occurrence of any new AEs/SAEs will be assessed.

EOS = end of study; FU = follow-up; Tx = Treatment; V = visit

2.7. Schedule of Assessments for Cohort 6

Activities	Screening 28 days		7	Freatme	nt Perio lays	d							Follo	ow-Up Perio	od
Visit Number	Screening	1	2	3	4	5	6	7	8	9	10	11	12	13	14
Visit	Screening	Tx Visit 1	Tx V1 FU1	Tx V1 FU2	Tx V1 FU3	Tx V1 FU4	Tx V1 FUS	Tx Visit 2	Tx V2 FU1	Tx V2 FU2	Tx V2 FU3	Tx V2 FU4	90 Day Follow-Up Visit	135 Day Follow-Up Visit	EOS / ET Visit°
Visit Windows (Days)	(Day -28 to Day -1)	Day 1	1 to 2 Days After TV1	3 to 5 Days After TV1	6 to 9 Days After TV1	10 to 14 Days After TV1	18 to 24 Days After TV1 (Day 22 ± 3 Days)	Day 43 (±3 Days)	1 to 2 Days After TV2	3 to 5 Days After TV2	6 to 9 Days After TV2	10 to 14 Days After TV2	Day 90 (±7 Days)	Day 135 (±7 Days)	Day 180 (±7 Days)
Informed consent ^a	X														
Inclusion/Exclusion criteria review	X	Xb													
Clinician Reported Photonumeric Cellulite Severity Scale (CR-PCSS) ^{c,d}	X	Xb													
Hexsel Cellulite Severity Scale (CSS) ^{c,d}	X	Xb													
Cohort assignment ^e		X													
Medical and surgical historyf	X														
Cellulite history	X														
Physical examination (including height)	X														
Weight	X	X													X
Fitzpatrick Skin Type d	X														
Vital signs	X	Xg						Xg							X
Clinical laboratory tests (chemistry, hematology, urinalysis)	X														X

Activities	Screening 28 days		7		nt Perio	d								ow-Up Perio 90 days	od
Visit Number	Screening	1	2	3	4	5	6	7	8	9	10	11	12	13	14

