4. OBJECTIVES AND ENDPOINTS

4.1. Objectives and Endpoints

Objectives	Endpoints
Primary	
To assess the effects of interventions on bruising of the buttocks of participants with cellulite after the first treatment with QWO (CCH-aaes).	 Cohorts 1 to 6: The proportion of participants whose left buttock (investigational side) demonstrates at least 1-level lower score versus the right buttock (control side) on the Investigator Assessment of Bruising Severity Scale (IABSS), at Visit 3, three to 5 days after initial QWO (CCH-aaes) injection. The IABSS is a 5-point scale ranging from 0-4, with 0 indicating no bruising or almost none, and 4 indicating very severe bruising. Cohort 7a: The proportion of participants whose left buttock (investigational side), at Visit 3, demonstrates at least 1-level lower score versus the right buttock (control side), at Visit 8 on the Investigator Assessment of Bruising Severity Scale (IABSS). These visits are three to 5 days after initial QWO (CCH-aaes) injection for each respective buttock. Cohort 7b: The proportion of participants whose left buttock (investigational side), at Visit 8, demonstrates at least 1-level lower score versus the right buttock (control side), at Visit 3, on the Investigator Assessment of Bruising Severity Scale (IABSS). These visits are three to 5 days after initial QWO (CCH-aaes) injection for each respective buttock.
Secondary	,
To assess the effects of interventions on bruising of the buttocks of participants with cellulite after each treatment with QWO (CCH-aaes).	• The proportion of participants whose left buttock (investigational side) demonstrates at least 1 level lower score versus the right buttock (control side) on the IABSS, by visit. The IABSS is a 5-point scale ranging from 0-4, with 0 indicating no bruising or almost none, and 4 indicating very severe bruising.

Objectives	Endpoints

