7.1. Selection and Marking of Dimples

To ensure that the non-interventional buttock can serve as a control, and that a similar level of injection site bruising may be expected, participants should have a similar number of dimples requiring treatment on each buttock. Participants in Cohorts 1, 2, 3, 5, and 6 can be treated with up to 12 injections of QWO (CCH-aaes) on each buttock. The number of injections of QWO (CCH-aaes) administered to the right and left buttocks should be identical on Day 1. The number of injections may differ following the first treatment session, eg, 12 injections in each buttock in the first treatment session followed by fewer injections per buttock at the second and third treatment sessions as dimples improve.

Participants in Cohort 7 can be treated with up to 12 injections of QWO (CCH-aaes) on each buttock. Dimples will only need to be marked on the days of treatment. In Cohort 7a, on Day 1 only, the investigational buttock will be treated with QWO (CCH-aaes) and on Day 64 only the control buttock will be treated with QWO (CCH-aaes). On Days 22 and 43, both buttocks will be treated with QWO (CCH-aaes). In Cohort 7b, on Day 1, only the control buttock will be treated with QWO and on Day 64, only the investigational buttock will be treated with QWO (CCH-aaes). On Days 22 and 43, both buttocks will be treated with QWO (CCH-aaes).

For treatment, a qualified designated physician will select up to 12 dimples within each treatment area (each buttock) that are well-defined, evident when the participant is standing, and suitable for treatment.

For each dimple selected for treatment, a qualified designated physician will choose injection sites (injection sites within a dimple should be spaced approximately 2 cm apart, if a dimple requires more than 1 injection; locating at least 1 injection site at the nadir, if present, of the dimple). Each injection site will be marked with a "dot" using a surgical marker. For round dimples, the "dot" will be placed in the center of the dimple; for elongated dimples, "dots" will be spaced out approximately 2 cm along the longer axis of the dimple. The qualified designated physician will then use a surgical marker to circle each of the dimples selected for treatment.

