8. DISCONTINUATION FROM STUDY INTERVENTION AND STUDY WITHDRAWAL

8.1. Discontinuation of Study Intervention

In certain instances, it may be necessary for a participant to be permanently discontinued from study intervention (QWO [CCH-aaes]) by the investigator or the sponsor. Treatment may be discontinued at the discretion of the investigator for safety, behavioral, or compliance reasons. This is expected to be uncommon.

Participants who request to discontinue study intervention will be encouraged to complete the remaining study visits and evaluations and provide any additional follow-up information as required by the study. Participants who discontinue from the study intervention and do not agree to remain in the study for follow-up, will be requested, (if applicable) to complete an ET visit and a 28-day post-treatment Safety Follow-up Visit (or phone call if a visit is not possible), if applicable. During this visit, the status of any ongoing AEs/SAEs, or the occurrence of any new AEs/SAEs will be recorded.

The date of and reason for discontinuation of study intervention will be recorded.

Participants who discontinue from study intervention at any time after the first dose of study QWO (CCH-aaes) will not be replaced.

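### Later-session IABSS proportions count attending participants who were not injected at that session, so they mix the effect on bruising with the rate of stopping QWO; the Cohort 7 primary endpoint is exposed too

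*SAP*

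**What the plan says.** **Objective.** The secondary bruising objective in Protocol 4.1 concerns "participants with cellulite after each treatment with QWO (CCH-aaes".

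**Who keeps attending.** Protocol 8.1: "Participants who request to discontinue study intervention will be encouraged to complete the remaining study visits and evaluations". The footnote to the Cohorts 1-5 schedule (Protocol 2.6) agrees: "Participants are encouraged to remain in the study for follow-up until the Day 180 Visit". That schedule has IABSS at every treatment visit and at all four follow-ups after it.

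**Who is counted.** The FAS (SAP 5) needs only one valid IABSS after any injection, not one per session. SAP 6.1 takes participants with a non-missing value at the visit as the denominator.

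**What is tabulated.** SAP 7.6.2.1 specifies "In Cohort 1-6, proportion of one-level IABSS responders at each visit", and "For Cohort 1-5, the summary tables will be given for Visit 2-Visit 15 and for Cohort 6 it will be for Visit 2-Visit 11". SAP 7.6.2.2 covers Visits 2 to 20 for Cohort 7. SAP 7.6.1.1 adds IABSS ratings by treatment area at each visit.

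**Responder rule.** SAP 4.5.1 requires that the left buttock "demonstrates at least a 1-level lower IABSS score versus the right buttock (control side) at Visit B". Equal scores are therefore a non-response.

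**Estimand.** Both secondary IABSS estimands state "Intercurrent Event: Not applicable". So do the Cohort 7 primary estimands in SAP 7.6.1.2 and 7.6.1.3.

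**The concern.** A participant who has stopped injections but still comes to the visits tied to session 2 or 3 has no new injection bruise on either side. Under the rules above she is nevertheless rated, enters the denominator and, with equal scores, counts against the intervention. She also adds a zero to each side of the severity tables, which makes bruising look milder than it is in injected buttocks. The endpoint is meant to describe bruising after a treatment, and she had none.

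Stopping could plausibly follow severe bruising in an open-label trial and could differ between cohorts. The later-session proportions would then carry that difference along with any difference in bruising.

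The SAP itself foresees the event. It plans counts of TEAEs leading to interruption or discontinuation of the intervention (7.7.2) and numbers treated at each visit by side (7.7.1). Yet no estimand says how IABSS scores after a missed session are handled.

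**Working it through.** **The plan's own figures.** 7 cohorts x 30 = 210 enrolled; 168/210 = 80%, or 24 of 30 per cohort; 210 - 168 = 42 non-completers, 20%. This 20% does not estimate the quantity needed here. Protocol 5.5 defines a completer as someone who completes Day 180, so a participant who stops injections and attends to the end is a completer. The 42 are people who leave, and they drop out of a non-missing denominator.

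**Visits affected in Cohorts 1-5.** Visit 6 (Day 22) is rated before injection and still reflects session 1. For someone who stops after session 1, the affected visits are 7 to 15, which is 9 of the 14 tabulated. For someone who misses only session 3, they are Visits 12 to 15. In Cohort 6, missing the second session affects Visits 8 to 11.

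**Formula.** Let p be the responder proportion among those injected, d the fraction of rated participants not injected, and q the responder proportion among those not injected. The table shows p(1-d) + qd. Protocol 5.2 says bruising resolves within 21 days in most participants, so an uninjected session is expected to give about 0 on both sides. That means q is about 0, and the table shows p(1-d).

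**Results.** No document gives p or d for this group; both are assumptions.

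| p | d = 5% | d = 10% | d = 20% |
|---|---|---|---|
| 30% | 28.5% | 27% | 24% |
| 50% | 47.5% | 45% | 40% |
| 70% | 66.5% | 63% | 56% |

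At d = 20% the shift is 6 to 14 points. At p = 50% and d = 5% it is 2.5 points, or 0.75 of a participant in 30.

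**Worked case with the SAP's Clopper-Pearson interval.** Thirty attend, 6 of them not injected, and 12 of the 24 injected respond. As planned: 12/30 = 40.0% (22.7 to 59.4). Among the injected: 12/24 = 50.0% (29.1 to 70.9). With nobody stopping, the 95% half-width at n = 30 is about 17 points at p = 30% or 70% and about 19 at p = 50%.

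**Cohort 7 primary.** Doses are staggered (Protocol 5.3, Figure 1), so the pair compared is not uninjected on both sides.

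- 7b compares the left side at Visit 8 with the right at Visit 3. A participant who stops after Day 1 but attends Visit 8 has a bruised control score and a never-injected investigational side expected to score 0. If the control scored 1 or more, she is a responder.
- 7a compares the left at Visit 3 with the right at Visit 8. A participant who stops after Day 1 has a never-injected control side. If it scores 0, nothing can be lower, so she cannot respond.

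Each case carries 1/15 = 6.7 points of the tabulated proportion. With 7 responders among 14 injected (50%), one such case gives 8/15 = 53.3% in 7b or 7/15 = 46.7% in 7a, a net shift of 3.3 points either way. Later dose pairs behave the same way when the second side to be dosed misses its dose.

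**The case against.** The strongest reply is that this is small and partly a matter of choice.

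- **Frequency.** Protocol 8.1 expects stopping led by the investigator or sponsor to be uncommon, and participants who ask to stop are only encouraged to stay. This stands as a limit on size. No rate is given for requested stopping, and at plausible low rates the shift is well inside sampling error. A wide interval does not remove a bias, however.
- **Treatment policy.** A by-visit summary of all attenders can be a legitimate description, and restricting to the injected selects those who continued. The selection point stands and shapes the fix. But the SAP names no strategy, and an uninjected pair has no post-injection bruise to compare.
- **Cohort 7 wording.** SAP 7.6.2.2 already pairs doses by number, so a participant without a second dose arguably has no second-dose comparison. That helps, but the method line tabulates Visits 2 to 20 with no exclusion, and the primary is defined by visit.
- **Undefined terms.** Follow-up windows are anchored to the treatment visit, so rating times after a missed session are unclear. The words valid and evaluable in SAP 5 and 6.1 might be used to exclude such scores, and the table shells in Module 2 are not available here. Nothing visible does exclude them.
- **Transparency.** SAP 7.7.1 shows numbers treated per visit and side. A reader could see the problem there, but the proportion is not corrected.

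Two stronger readings are tempting and not supported. First, Protocol 7.1 says "The number of injections may differ following the first treatment session", from which a reader might infer that one side will be left uninjected once its dimples clear. The text speaks of fewer injections per buttock, not of skipping a side. Second, a reader might infer that cohorts will be misranked. The visible secondary analysis is descriptive within each cohort and plans no ranking.

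**Conclusion.** The point holds. In Cohorts 1-6 the planned later-session responder proportions are p(1-d) instead of p, and the severity tables gain zeros from uninjected buttocks. The size cannot be fixed from the documents. At p = 50% it is 2.5 points for d = 5% and 10 points for d = 20%, below the interval half-width in one cohort but always downward when the uninjected score equal on both sides.

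In Cohort 7 the direction depends on the sub-cohort, upward in 7b and downward in 7a, and the primary endpoint is exposed. The primary in Cohorts 1-6, at Visit 3 after the first session, is not affected.

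A reader might conclude that the later-session proportions follow stopping instead of the intervention. That goes too far: p(1-d) still scales with p, so the two are mixed. Protocol 5.2 also says bruising itself lessens after the second and third sessions, so a change across sessions has more than one cause.

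The conclusion assumes that some participants stop and still attend, that they are rated, and that earlier bruises have resolved.

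**What to change.** In SAP 7.6.2.1 and 7.6.2.2, and for the Cohort 7 primary in 7.6.1.2 and 7.6.1.3:

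1. Replace the intercurrent-event entry with stopping or missing QWO at a session, and state that the post-injection outcome is not defined for a session not received.
2. Compute each session's post-injection responder proportion and severity table among FAS participants injected on both buttocks at the session being compared. In Cohort 7, use the dose number being compared on each side.
3. Beside each proportion, show the number not injected, by side and reason.
4. Keep the all-attender by-visit figure as a supportive line, so that the effect of the restriction is visible.

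The cost is SAP wording and one programming flag from exposure data that SAP 7.7.1 already summarises by visit and side. Protocol 8.1 already records the reason for discontinuing the intervention; the reason for a single missed session may need checking in the eCRF. The downside is smaller denominators at later sessions and a population limited to those who continued treatment, which items 3 and 4 make explicit.
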